3.8.1.5 Handling missing month/day in date of death

For rare cases when either day is missing or both month and day are missing for the date of death, the imputation rules in section 3.8.2.1 will be implemented.

3.8.2 Secondary efficacy analyses

The secondary efficacy objectives in this study are to

- compare the two treatment arms with respect to overall survival
- evaluate the two treatment arms with respect to overall response rate and clinical benefit rate, time to response and duration of response;
- evaluate the two treatment arms with respect to time to deterioration of ECOG performance Status;
- evaluate patient reported outcomes for health-related quality of life in the two treatment arms.

The analysis of all secondary efficacy endpoints will be performed based on the FAS.

3.8.2.1 Overall survival

Comparing the overall survival (OS) between ribociclib +fulvestrant and placebo+fulvestrant is a secondary objective in this study. OS is defined as the time from date of randomization to date of death due to any cause. If a patient is not known to have died at the time of analysis

cut-off, then OS will be censored at the date of last contact. Assuming proportional hazards for OS, the following statistical hypotheses will be tested:

$$H_{02}: \theta_2 \geq 0 \text{ vs. } H_{A2}: \theta_2 < 0$$

Where θ_2 is the log OS hazard ratio (fulvestrant+ ribociclib arm vs. fulvestrant + placebo arm). The analysis to test this hypothesis is a stratified log-rank test at an overall one-sided 2.5% level of significance. The stratification will be based on the randomization stratification factors.

A maximum of 3 analyses are planned for OS: at the time of the analysis for PFS (provided PFS is significant), at which point a total 161 deaths (46% of OS events) are expected, after 263 events (75% of OS events) have been documented, and a final analysis for OS when 351 deaths (100% of OS events) are expected (expected 56 months from date of first patient to be randomized).

OS tests will be carried out using a Lan-Demets (O'Brien-Fleming) alpha spending function. OS will only be tested if the primary efficacy analysis has been shown to be statistically significant. Analyses will be based on the FAS population according to the randomized treatment group and strata assigned at randomization. All deaths recorded up to the cut-off date will be included in the analysis. The survival distribution of OS will be estimated using the Kaplan-Meier method, and Kaplan-Meier curves, medians and 95% confidence intervals of the medians intervals along with the proportion of patients alive at 6 month interval starting from 12 month will be presented for each treatment group. The hazard ratio for OS will be calculated, along with its 95% confidence interval, using a stratified Cox model using the same stratification factors as the log-rank test.

If OS is statistically significant, a stratified multivariate Cox proportional hazard model adjusting for covariates will be fitted, including the treatment arm and the following key potential prognostic factors as covariates: age (≥ 65 vs < 65), prior chemo therapy in (neo)adjuvant setting (yes vs no), ECOG performance status (0 vs. 1), and bone only lesion at baseline (yes or no). In addition, stratified multivariate Cox models will be fitted including treatment arm and each of these factors individually, including treatment by factor interaction, to explore the relationship between each factor and treatment.

[REDACTED]

The pattern of censored data will be examined between the treatment arms: reasons for censoring ('Alive' or 'Lost to follow-up') and death cause will be summarized by treatment arm. In addition, survival status, reason for censoring and death cause will be listed. Patients not known to have died will be censored as 'Lost to follow-up' if the time between their last contact date and the analysis cut-off date is longer than the protocol specified interval between the survival follow-up assessments plus 2 weeks, i.e., 14 weeks (98 days) for this study.

Handling missing month/day in date of death

For rare cases when either day is missing or both month and day are missing for the date of death, the following imputation rules will be implemented:

- If only day is missing, then date of death is imputed as max [(1 mmm-yyyy), min(last contact date +1, cutoff date)].
- If both day and month are missing, then date of death is imputed as max [(1 Jan-yyyy), min (last contact date +1, cutoff date)].

3.8.2.2 Overall response rate

ORR is defined as the proportion of patients with best overall response of confirmed complete response (CR) or confirmed partial response (PR) according to RECIST 1.1 ([\[see Appendix 2 of the study protocol\]](#)). ORR will be calculated based on the FAS using investigators' review of tumor assessment data. Patients with only non-measurable disease at baseline will be part of the analysis and will be included in the numerator only if a complete response was observed. ORR will be presented by treatment arm along with standard Wald asymptotic (i.e. normal approximation) 95% confidence intervals. The Cochran-Mantel Haenszel chi-square test (strata based on IRT data) will be used to compare the two treatment arms with respect to the ORR at a one-sided 2.5% level of significance.

As a supportive analysis, ORR will also be summarized based on the BIRC review of tumor data. As a sensitivity analysis, ORR will be calculated and summarized for patients with only measurable disease at baseline.

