## 10.5 Secondary objectives

The secondary objectives in this study are to compare the two treatment groups with respect to overall survival (OS), and evaluate overall response rate (ORR), clinical benefit rate (CBR), time to response (TOR), duration of response (DOR) and time to definitive deterioration in the quality of life and ECOG PS, safety. OS between the 2 treatment arms will be statistically compared. A hierarchical testing strategy will be taken to control overall type-I error rate; therefore OS will be statistically evaluated and interpreted only if the primary efficacy endpoint PFS is significantly different between the 2 treatment groups.

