## **10.5.2 Other secondary efficacy objectives**

### **10.5.2.1 Overall response rate**

Overall response rate (ORR) is defined as the proportion of patients with best overall response (BOR) of complete response (CR) or partial response (PR) according to RECIST 1.1.

ORR will be calculated based on the FAS according to the ITT principle; however patients with only non-measurable disease at baseline will be included in the numerator if they achieve a complete response. ORR will be presented by treatment group along with approximate 95% confidence intervals. The Cochran-Mantel Haenszel chi-square test (stratified by baseline stratification factor) will be used to compare the two treatment groups with respect to the ORR at one-sided 2.5% level of significance. As a supportive analysis, ORR as assessed by the blinded independent central review will be calculated by treatment group and presented along with the approximate 95% confidence intervals. As a sensitivity analysis, ORR for patients with measurable disease at baseline will be calculated and presented by treatment group together with approximate 95% confidence intervals.

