### **10.5.2.2 Clinical benefit rate**

Clinical Benefit is defined as CR, PR or SD for 24 weeks or longer. CR, PR and SD are defined according to RECIST 1.1. CBR will be calculated based on the FAS; however patients with only non-measurable disease at baseline will be included in the numerator if they achieve a complete response. CBR will be summarized for the two treatment groups using descriptive statistics. The Cochran-Mantel Haenszel chi-square test (stratified by baseline stratification factor) at 2.5% one-sided level of significance, will be used to compare the two treatment groups with respect to the CBR. As a supportive analysis, CBR as assessed by the blinded independent central review will be summarized for the two treatment groups using descriptive statistics.

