### **10.5.2.5 ECOG performance status**

ECOG PS scale as described in [Section 7.2.2.4](#) will be used to assess physical health of patients. An analysis of time to definitive deterioration of the ECOG PS by one category of the score from baseline will be performed. Deterioration is considered definitive if no improvements in ECOG PS status is observed at a subsequent time of measurement during the treatment period following the time point where the deterioration is observed.

Patients receiving any further therapy prior to definitive worsening will be censored at their date of last assessment prior to start of therapy. Patients that have not worsened at the data cut-off point will be censored at the date of last assessment prior to start of therapy. Kaplan-Meier method will be used to estimate the distribution of time to definitive worsening and median time to definitive worsening will be presented along with a 95% confidence interval. A stratified log-rank test at one-sided 2.5% level of significance will be used to compare the distribution of time to definitive worsening between the 2 treatment arms.

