### **10.7.2 Overall survival (OS)**

OS will be compared between the two treatment groups, provided the primary endpoint PFS is statistically significant favoring the test treatment arm (ribociclib + fulvestrant). A gatekeeping testing procedure will be adopted in this study and the OS analyses will be performed only if the primary efficacy endpoint PFS is statistically significant. A maximum of 3 analyses is planned for OS; at the time of the final analysis for PFS (provided PFS is significant), at which point approximately 161 deaths are expected, after approximately 263 events have been

documented), and a final analysis for OS when approximately 351 deaths are expected (expected 56 months from date of first patient to be randomized).

An  $\alpha$ -spending function according to Lan-DeMets (O'Brien-Fleming) independent of the one used for the primary efficacy analysis, (as implemented in East 6.3) along with the testing strategy outlined below will be used to maintain the overall type I error probability (Lan and DeMets 1983). This guarantees the protection of the 2.5% overall level of significance across the two hypotheses and the repeated testing of the OS hypotheses in the interim and the final analysis (Glimm 2010). The trial allows for the stopping of the study for a superior OS result, provided the primary endpoint PFS has already been shown to be statistically significant favoring the test treatment arm (ribociclib +fulvestrant). Further, the exact nominal p-values that will need to be observed to declare statistical significance at the time of these analyses for OS will depend on the number of OS events that have been observed at the time of these analyses and the  $\alpha$  for OS already spent at the time of earlier analyses.

The projected timing of interim analysis is summarized in Table 10-1.

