3.8.2.3 Clinical benefit rate

CBR is defined as the proportion of patients with a best overall response of confirmed CR or PR, or SD lasting 24 weeks or longer, according to RECIST 1.1 criteria. A patient will be considered to have SD for 24 weeks or longer if a SD response is recorded at 24-1=23 weeks or later from randomization, allowing for the ± 1 week visit window for tumor assessments. Patients with only non-measurable disease at baseline will be part of the analysis and will be included in the numerator only if they achieve a complete response or have a 'Non-CR/Non-PD' response 23 weeks or more after randomization. CBR will be calculated using the FAS based on the investigators' tumor assessments. CBR will be summarized for the two treatment arms using descriptive statistics. The Cochran-Mantel-Haenszel test (strata based on IRT data) at one sided 2.5% level of significance will be used to compare the two treatment arms with respect to CBR. CBR based on (1) BIRC review, and (2) only including patients with measurable disease at baseline, will be summarized for the two treatment arms using descriptive statistics.

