If a definitive deterioration is observed after two or more consecutive missing assessments, time to deterioration will be censored at the date of the last ECOG PS assessment prior to the deterioration. The number of missing assessments is calculated based on the time window in Table 3-4 and a rule similar for tumor assessments (see detail in section 2.5.5).

Patients receiving any further anti-neoplastic therapy before definitive deterioration will be censored at the date of their last assessment before the start date of the therapy. Patients that have not worsened as of the cutoff date will be censored at the date of their last assessment before the cutoff.

Kaplan-Meier estimates will be constructed for each treatment arm. The median, 25th and 75th percentiles for time to definitive deterioration for each treatment group will be obtained along with 95% confidence intervals.

A stratified log-rank test at one-sided 2.5% level of significance will be used to test the difference in time to definitive worsening of performance status between treatment arms. A (stratified) Cox proportional hazards model will be used to estimate the hazard ratio (with 95% confidence interval).

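### ORR, CBR and time to ECOG deterioration are each tested at one-sided 2.5% outside the PFS-then-OS hierarchy and with no nominal label, so significance claims on them have no type I error control

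*SAP*

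**What the plan says.** Three secondary endpoints other than OS carry a test at the full one-sided 2.5% level, and the two documents agree on each.

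- **ORR.** SAP 3.8.2.2 uses a Cochran-Mantel-Haenszel test to "compare the two treatment arms with respect to the ORR at a one-sided 2.5% level of significance". Protocol 10.5.2.1 uses it to "compare the two treatment groups with respect to the ORR at one-sided 2.5% level of significance".
- **CBR.** SAP 3.8.2.3 says the same test at a one-sided "2.5% level of significance will be used to compare the two treatment arms with respect to CBR". Protocol 10.5.2.2 sets a "2.5% one-sided level of significance, will be used to compare the two treatment groups with respect to the CBR".
- **Time to definitive ECOG deterioration.** SAP 3.8.2.6: "A stratified log-rank test at one-sided 2.5% level of significance will be used to test the difference in time to definitive worsening". Protocol 10.5.2.5: "A stratified log-rank test at one-sided 2.5% level of significance will be used to compare the distribution of time to definitive worsening".

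On error control, Protocol 10.5 states: "A hierarchical testing strategy will be taken to control overall type-I error rate". The consequence it draws concerns OS alone, which is interpreted only if PFS is significant. The same paragraph says that OS will be statistically compared and that the other secondaries will be evaluated. Protocol 10.7.2, with SAP 3.14.2 to the same effect, sets the scope: "This guarantees the protection of the 2.5% overall level of significance across the two hypotheses", meaning PFS and OS with its repeated looks.

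On patient-reported outcomes, Protocol 10.5.5 rules out formal tests and gives that as the reason for making no multiplicity adjustment. SAP 3.8.2.7 nevertheless compares time to 10% deterioration in global health status, and in the secondary PRO scales, by stratified log-rank test at two-sided 5%.

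**The concern.** Naming a test and a significance level sets a decision rule. As written, ORR, CBR and ECOG deterioration may each be declared significant against the threshold used for PFS, whatever PFS or OS shows. Nothing orders the three tests, gates them, divides alpha among them or marks them as nominal. OS, by contrast, has an explicit gate and its own spending function.

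Elsewhere the authors do mark status. SAP 3.8.1.4 says that no p-value will be shown for the derived-response Cox model or the by-stratum hazard ratios, and that the CRF-strata model yields no other inferential statistics.

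What is at stake is how the secondary results are described. A delay in ECOG deterioration or a gain in CBR reported as statistically significant would read as confirmatory alongside PFS and OS, although no procedure in the plan supports that status.

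**Working it through.** **1. The plan's own figures.**

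PFS: power = Φ(√(d·p(1−p))·|ln HR| − 1.96), with d = 364, p = 2/3 (2:1 allocation) and HR 0.67. This gives √(364 × 2/9) = 8.99; 8.99 × 0.4005 = 3.60; Φ(3.60 − 1.96) = 0.950. That matches the 95% in Protocol 10.8 and SAP 3.16.

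OS: the SAP 4.3.1 spending function, α(t) = 2 − 2Φ(z/√t) with z the upper 1.25% normal point, at t = 161/351, 263/351 and 1.

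| Deaths | Cumulative one-sided alpha | Power at HR 0.71, recomputed | Power stated |
|---|---|---|---|
| 161 | 0.0009 | 14.4% | 14% |
| 263 | 0.0096 | 60.7% | 60% |
| 351 | 0.0250 | 85.0% | 85% |

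The error control for PFS and OS reproduces. The documents give no error rate for ORR, CBR and ECOG taken together, so there is no stated figure to check for them.

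**2. Three tests at 0.025, all nulls true.**

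- Independent tests: 1 − (1 − 0.025)³ = 1 − 0.9269 = 7.3%.
- Bonferroni ceiling: 3 × 0.025 = 7.5%.

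**3. Allowing for correlation.**

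Every ORR responder is also counted in CBR. For nested proportions p₁ ≤ p₂ the correlation is √[p₁(1−p₂)/(p₂(1−p₁))]. The documents give neither response rates nor correlations, so both are assumed here. The rate is the probability that at least one of three jointly normal statistics exceeds 1.96.

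- Example: ORR 30%, CBR 65%. Correlation = √(0.30 × 0.35/(0.65 × 0.70)) = √(0.105/0.455) = 0.48. With ECOG correlated 0.2 with each, the rate is 6.8%.
- Ten assumed pairs, with ORR 10–50% and CBR 50–80%, give ORR–CBR correlations of 0.25 to 0.67. With the ECOG correlation between 0 and 0.5, the rate runs from 6.0% to 7.2%.
- One common correlation for all three tests:

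| Common correlation | 0 | 0.3 | 0.5 | 0.7 | 0.9 |
|---|---|---|---|---|---|
| At least one false significance | 7.3% | 6.8% | 6.3% | 5.5% | 4.2% |

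**4. What control would require.** Bonferroni would put each test at 0.025/3 = 0.0083 one-sided. A fixed order after OS, each at 0.025 and stopping at the first failure, would also hold 2.5%. Labelling the tests nominal changes no number; it removes the claim.

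**5. PRO tests.** Protocol 10.5.5 and SAP 3.8.2.7 contradict each other. The PRO tests are not in the count above. They enlarge the set of uncontrolled tests, but without information on how the scales correlate no useful combined rate can be given.

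**The case against.** The strongest reply is that this is a missing label. Protocol 10.5 separates OS, which is compared, from the other secondaries, which are evaluated. Formal hypotheses and power are written only for PFS and OS. The sentence on hierarchical control leads straight to OS, and SAP 3.8.2 itself makes no claim of overall error control. An informed reader could take the three tests as nominal.

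Much of that stands. In particular, a reader might infer that the trial's 2.5% guarantee has been inflated to about 6%. The documents do not support this: they promise 2.5% for PFS and OS only, that promise is unaffected, and no rate is stated for the three other endpoints that could be exceeded.

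The reply does not dispose of the point, because the evaluate wording and the explicit significance level conflict. Six sections set the level, and none says that the result is nominal. The SAP sentence about tests that merely explore the data sits under other safety data (3.9.7) and does not clearly reach these efficacy tests.

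Two further objections also have weight. Labelling is uneven elsewhere: SAP 3.8.1.4 repeats log-rank tests for PFS sensitivity analyses without a nominal label. Those, however, re-examine a hypothesis already tested and do not open a new claim. Practical reach is also limited. Protocol 10.7.2 makes analyses after amendment 4 descriptive, and the final-report SAP contains no ORR, CBR or ECOG tests. Nor do the documents show that a significance claim was made on any of the three.

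**Conclusion.** The point holds as a gap in the status of these tests. ORR, CBR and time to definitive ECOG deterioration each carry a full one-sided 2.5% test with no place in the hierarchy and no nominal label, so a significance claim on any of them is uncontrolled.

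If all three nulls are true, the chance of at least one false significance is 7.3% under independence, about 6–7% allowing for ORR/CBR overlap, and 4.2% at a common correlation of 0.9. Only the independence figure follows from the stated levels alone; the others rest on assumed response rates and correlations.

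A reader might also infer a larger rate by adding PFS to the count as a gate. That does not follow. Counting PFS that way treats it as a fourth ungated test, whereas a real PFS gate would hold the rate at or below 2.5% when all nulls, PFS included, are true. The plan writes no such gate for these three endpoints. A PFS gate alone would not control them when PFS truly improves, because the gate would then usually be open.

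The PFS and OS conclusions are untouched. This is a cheap improvement, confined to the primary-analysis SAP, the matching protocol sections and the reporting of that analysis.

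**What to change.** In Protocol 10.5.2.1, 10.5.2.2 and 10.5.2.5 and SAP 3.8.2.2, 3.8.2.3 and 3.8.2.6, delete the words that set a one-sided 2.5% significance level. State instead that these endpoints lie outside the type I error control and are reported as estimates with 95% CIs and nominal p-values, with no claim of statistical significance. Bring SAP 3.8.2.7 into line with Protocol 10.5.5 in the same way, by removing the two-sided 5% level for the PRO comparisons. Wherever the primary-analysis results are reported, carry the same statement as a table footnote.

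Had a confirmatory claim on any of the three been wanted, it would have needed a pre-specified place after OS in a fixed sequence, or a share of alpha.

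The cost is a sentence in each of the six sections, a matching edit for PRO, and footnotes. The sponsor gives up the word significant for these endpoints. Estimation methods, sample size and the PFS and OS tests do not change.

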3.8.2.3 Clinical benefit rate

CBR is defined as the proportion of patients with a best overall response of confirmed CR or PR, or SD lasting 24 weeks or longer, according to RECIST 1.1 criteria. A patient will be considered to have SD for 24 weeks or longer if a SD response is recorded at 24-1=23 weeks or later from randomization, allowing for the ± 1 week visit window for tumor assessments. Patients with only non-measurable disease at baseline will be part of the analysis and will be included in the numerator only if they achieve a complete response or have a 'Non-CR/Non-PD' response 23 weeks or more after randomization. CBR will be calculated using the FAS based on the investigators' tumor assessments. CBR will be summarized for the two treatment arms using descriptive statistics. The Cochran-Mantel-Haenszel test (strata based on IRT data) at one sided 2.5% level of significance will be used to compare the two treatment arms with respect to CBR. CBR based on (1) BIRC review, and (2) only including patients with measurable disease at baseline, will be summarized for the two treatment arms using descriptive statistics.

3.8.2.4 Time to response

Time to response (CR or PR) is the time from date of randomization to first documented response (CR or PR, which must be confirmed subsequently) according to RECIST 1.1. All

patients in the FAS will be included in the time to response calculation. Patients without confirmed PR or CR will be censored at:

- the maximum follow-up time (i.e. FPFV to LPLV used for the analysis) for patients who had a PFS event (i.e. either progressed or died due to any cause);
- the last adequate tumor assessment date for all other patients.

Time to response data will be listed and summarized by treatment arm. The distribution of time to response will be estimated using the Kaplan-Meier method and the median time to response will be presented along with 95% confidence interval only if a sufficient number of responses are observed. A descriptive summary of time to response for the responders will also be presented.

